## **6 SIGNIFICANCE LEVEL**

A significance level of 0.05 (2-sided) will be used. All analyses will be performed using IBM SPSS Statistics 25 and/or SAS 9.4 and/or JMP 14.

## **7 APPENDIX**

### **7.1 Definition of Responders**

For HAM-D17, HAM-D6, QIDS-SR6, HAMD-6, PHQ-9, GAD-7, SF-36, a responder is defined as a participant with 50% decrease from baseline in total scale score.

For Clinical Global Impression: Severity of Illness CGI-S: a responder is defined as a decrease in category of severity of at least 1 point, for Clinical Global Impression: Global Improvement CGI-I: it's defined as a score from 1 to 3, and for Clinical Global Impression: Efficacy Index CGI-EI: it's defined as scores of 01, 02, 05, or 06.

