8.2.2 Clinical Outcome Measures of Health Related Quality of Life

i. EuroQol (EQ-5D-5L)

The EQ-5D is designed for self-completion and assesses health across five domains: mobility, self-care, usual activities, pain/discomfort, and anxiety/depression. In the 5-level versions of EQ-5D (EQ-5D-5L), each domain has five levels of severity; health 'today' is assessed (See Appendix IX). The EQ Visual Analogue scale (EQ VAS) is a single 20 cm vertical visual analogue scale, with a range of 0 to 100, where 0 is the worst and 100 is the best imaginable health.

ii. Short Form (36) Health Survey (SF-36)

The SF-36 is a generic health status profile measure, consisting of eight dimensions: physical functioning, role-physical, bodily pain, general health, vitality, social functioning, role-emotional and mental health(25). These eight dimensions produced separate scores by taking a simple summation of individual item responses, and applying a linear transformation, in order to place them onto a 0 to 100 scale (see Appendix X).

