16.1.3 Continuous Outcomes

If the HAM-D₁₇ scores from baseline to end of Week 8 of the study meet the assumptions of ANOVA modeling, repeated-measure (i.e., mixed) ANOVA models will be used to model the outcome scores over time. This model accounts for a between-group and within-individual effect, which allows for the examination of average differences between groups while also accounting for the correlation between participant scores between each measurement. If the HAM-D₁₇ scores do not meet standard ANOVA assumptions, GEEs will be used to model repeated measurements of outcome scores over time, as these models are more robust to departures from the standard assumptions and also allow the investigator to specify the correlation structure of the repeated measurements. Mean symptom improvement for all continuous measures (i.e., depression scales) will be calculated using the standard formula $(\frac{y_2 - y_1}{y_1}) * 100$, where y_1 is the baseline score for each participant for each rating scale and y_2 is the 8 week score for each participant for each rating scale.

Two hypotheses related to the primary objectives will be tested, where μ_1 is the mean HAM-D₁₇ % symptom improvement in the GEN group, μ_2 is the mean HAM-D₁₇ % symptom improvement in the E-GEN group and μ_3 is the mean HAM-D₁₇ % symptom improvement in the TAU group.

Primary objective (1):

$$H_0: \mu_1 = \mu_2 = \mu_3$$

$$H_a: \mu_1 = \mu_2 > \mu_3$$

Primary objective (2):

$$H_0: \mu_1 = \mu_2 = \mu_3$$

$$H_a: \mu_1 < \mu_2 > \mu_3$$

For all continuous measures, a responder will be defined as a participant with 50% change from baseline in total scale score. Remitters at week 8 and at week 12 will be defined as HAM-D₁₇ ≤7 in each treatment group. Differential time to response/remission of depressive symptoms over 8 and 12 weeks will be plotted using Kaplan-Meier curves and Cox proportional hazard models will test the null hypothesis of no difference in time to response/remission between groups.

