### **2.1.4 Exploratory, Safety, and Tolerability Objectives**

- Mean percentage change in Generalized Anxiety Disorder 7-item (GAD-7) scale from baseline to end of Week 8, Week 12, Month 6, Month 9, Month 12;
- Percentage of responders and remitters at Week 8, Week 12, Month 6, Month 9, Month 12 on GAD-7 (see definition in 7.1 and 7.2);
- Change in SF-36 from baseline to end of Week 12, Month 6, Month 9, and Month 12;
- Percentage of responders at Week 12, Month 6, and Month 12 on SF-36 (see definition in 7.1);
- Mean percentage change in the Clinical Global Impression: Severity of Illness (CGI-S) from baseline to end of Week 12 and Month 12;
- Percentage of responders and remitters at Week 12 and Month 12 on CGI-S in each treatment group (see definition in 7.1 and 7.2);

- Percentage responders at Week 12 and Month 12 on CGI-I (Clinical Global Impression: Global Improvement) in each treatment group (see definition in 7.1);
- Percentage responders at Week 12 and Month 12 on CGI-IE (Clinical Global Impression: Efficacy Index) in each treatment group (see definition in 7.1);
- Compare congruence of medications between treatment groups at Week 8, Week 12, Month 6, Month 9, and Month 12 (see 7.5 for definition);
- Percentage of subjects who experienced adverse events (AE) at Week 8, Week 12, and Month 12;
- Change in Udvalg for Kliniske Undersogeler (UKU) side effect rating scale; Frequency, Intensity and Burden of Side Effects Ratings (FIBSER); and weight gain from baseline to Week 8, Week 12, and Month 12;
- Percentage of patients compliant with medications at Week 8, Week 12, Month 6, Month 9, and Month 12 between treatment groups using Brief Adherence Rating Scale (BARS) and prescription filling data

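### The SAP's SF-36 responder rule refers to a total score that neither document defines, and its direction of improvement is not stated (exploratory endpoint only)

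*SAP*

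**What the plan says.** SAP 7.1 sets one rule for seven listed scales: "For HAM-D17, HAM-D6, QIDS-SR6, HAMD-6, PHQ-9, GAD-7, SF-36, a responder is defined as a participant with 50% decrease from baseline in total scale score". It then gives CGI-S, CGI-I and CGI-EI rules of their own, but not the SF-36. SAP 2.1.4 plans the percentage of SF-36 responders at Week 12, Month 6 and Month 12 and points to 7.1 for the definition. SAP 2.2.3 and 5.2 list the same endpoint.

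Protocol 8.2.2 presents the SF-36 as a profile of eight dimensions: "These eight dimensions produced separate scores by taking a simple summation of individual item responses", followed by a linear transformation "in order to place them onto a 0 to 100 scale". It names no total or summary score. The protocol's own responder rule, in 16.1.3, is "For all continuous measures, a responder will be defined as a participant with 50% change from baseline in total scale score". That section glosses continuous measures as the depression scales.

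On visits, SAP 2.1.4 plans "Change in SF-36 from baseline to end of Week 12, Month 6, Month 9, and Month 12". For GAD-7 it plans mean percentage change on that "scale from baseline to end of Week 8, Week 12, Month 6, Month 9, Month 12", and responders and remitters at the same five visits.

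**The concern.** A responder rule needs a score, a direction and a threshold. For the SF-36 the SAP gives a threshold, but attaches it to a score that the protocol's description of the instrument does not contain. It takes its direction from symptom scales, on which a fall is an improvement. Whoever programs the endpoint would have to choose the score, and might have to reverse the direction, after the plan is final. At stake is the meaning of one exploratory quality-of-life result: the choice of score can change who counts as a responder, and the word *decrease* may point the wrong way.

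**Working it through.** The plan gives no figure to reproduce. The check sets the passages side by side and adds a short illustration.

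1. **Is a total defined anywhere?** Protocol 8.2.2 gives eight separate scores. Appendix X prints the questionnaire without a scoring key; its questions use different response formats, and question 9 mixes favourable items (feeling full of life) with unfavourable ones (feeling worn out), so an uncoded sum has no obvious meaning. SAP section 7 defines HAM-D6, congruence and BARS, but no SF-36 score. Protocol 16.1.3 does not fill the gap: it also needs a total, and SAP 1.2 says that the SAP supersedes the protocol's analysis plan.

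2. **Does the choice of score matter?** Question 3 in Appendix X has ten items with three response options. Assume that they are coded 1 to 3, so the raw sum runs from 10 to 30 and the 0–100 score is (raw − 10) / 20 × 100. Take a fall in the raw sum from 20 to 15.
   - Raw: (15 − 20) / 20 = −25%, not a responder.
   - Transformed: 50 to 25, and (25 − 50) / 50 = −50%, a responder.

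   Percentage change is not preserved when a scale is shifted, so responder status can depend on a choice that the SAP does not make.

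3. **Does direction matter?** The documents do not state it. Assume that higher is better. A patient who falls from 50 to 25 has lost half the score and is a responder under SAP 7.1. A patient who rises from 25 to 50 has (50 − 25) / 25 = +100% and is not. If lower is better on the chosen score, the word *decrease* is right.

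4. **Is there other evidence of an oversight?** SAP 2.1.4 and 2.2.3 plan percentage change for the HAM-D, QIDS-SR, PHQ-9, GAD-7 and CGI-S, but plain change for the SF-36. A percentage-based responder rule does not fit that treatment.

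5. **Visit lists against the schedule** (Protocol Figure 1 and section 9.7, which agree):

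| Scale | Scheduled after baseline | In SAP 2.1.4 but not scheduled |
|---|---|---|
| SF-36 change | Week 12, Months 6 and 12 | Month 9 |
| SF-36 responders | Week 12, Months 6 and 12 | none |
| GAD-7 change, responders, remitters | Weeks 4, 8, 12; Month 12 | Months 6 and 9 |

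Both scales are also collected at an early termination visit, whenever that occurs. SAP 2.1.3 qualifies its long-term visit list by applicability to each scale; the 2.1.4 bullets carry no such qualifier.

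**The case against.** The strongest reply is that nothing important depends on this. The SF-36 and GAD-7 appear only among the exploratory variables. They feed neither the primary test, nor the ordered secondary analyses, nor the rule in SAP 2.1.2.2 for combining GEN and E-GEN. That stands, and it sets the severity.

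A second reply is that the protocol cites an SF-36 manual in its description of the instrument, and that the SAP is based on the protocol. The manual may settle how the dimensions are scored. It is not available here and the SAP does not cite it. This limits the claim: a reader might infer that the endpoint cannot be derived at all, but the documents support only that the score is not defined in them.

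Three further inferences are tempting and go too far.
- That the trial will report worsening as response. This requires both that higher means better, which the documents do not say, and that someone supplies a score. Most dimension names, such as vitality or general health, suggest that higher is better; bodily pain does not.
- That change in SF-36 is equally undefined. With eight separately scored dimensions described, the natural reading is change in each of them.
- That the visit mismatches would produce wrong results. A visit without data gives an empty cell, and SAP 5.2 analyses responders and remitters visit by visit, so other visits are not contaminated. Early termination records could also fall near Month 6 or 9, so no scheduled assessment is not quite the same as no data.

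**Conclusion.** The point holds for the SF-36 responder endpoint and is minor. The rule in SAP 7.1 requires a total that neither document defines, at all three visits where the endpoint is planned. This is a stated rule that fails when followed, rather than a missing detail. That conclusion rests only on the text of the two documents. The further consequence, that worsening would count as response, is conditional on higher scores meaning better health. The coding in the illustration is likewise an assumption; it serves only to show that the choice of score can change responder status.

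The visit lists are an editorial mismatch, confirmed by both Figure 1 and Protocol 9.7. No primary or ordered secondary conclusion is affected.

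**What to change.** Remove SF-36 from the responder lists in SAP 2.1.4, 2.2.3, 5.2 and 7.1. State in 5.2 that the SF-36 is analysed as change in each of the eight dimensions, as exploratory results, and say which direction is better for each. If the sponsor wants to keep a responder summary, the SAP must name the score, the direction and the threshold in advance. Changing *decrease* to *increase* would not be enough, because the score would still be undefined.

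As tidying, delete Month 9 from the SF-36 change bullet in SAP 2.1.4. Delete Months 6 and 9 from the two GAD-7 bullets, or add the applicability qualifier already used in 2.1.3.

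The cost is a few lines of the SAP and the matching derivation code, with no new data. One exploratory responder summary is lost, and eight dimension results have to be reported and read as exploratory.

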### **7.2 Definition of Remitters**

A remitter is defined as a participant at a post-treatment visit with HAM-D17  $\leq 7$ , HAM-D6  $< 5^2$ , QIDS-SR6  $\leq 5$ , PHQ-9  $< 5$ , GAD-7  $< 5$ , or CGI-S  $\leq 1$ .

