8.2 Secondary Outcome Measures

8.2.1 Clinical Outcome Measures of MDD Symptoms and Medication Side Effects

i. 16-Item Self-Report Quick Inventory of Depressive Symptomatology (QIDS-SR16)

The QIDS-SR16 is a patient reported measure designed to assess the severity of depressive symptoms(17, 18). The scale assesses the nine DSM-IV criteria symptom domains for major depression: sad mood, concentration, self-outlook, suicidal ideation, involvement, energy/fatigability, sleep disturbance (4 items: initial, middle, late insomnia, and hypersomnia), appetite/weight increase/decrease (4 items), and psychomotor agitation/retardation (2 items) (see Appendix III).

ii. 9-Item Patient Health Questionnaire (PHQ-9)

The PHQ-9 consists of nine questions, rated 0–3 according to the increased frequency of difficulty experienced in each area covered. Scores are self-rated by patients, with a possible range of 0–27, are summed and can then be interpreted as follows: no depression (0), minimal (1–5), mild (6–9), moderate (10–14), moderately severe (15–19), or severe (>20) depression (see Appendix IV).

iii. Generalized Anxiety Disorder 7-Item (GAD-7) Scale

The GAD-7 is a brief measure of symptoms of anxiety, based on diagnostic criteria described in DSM-IV(19). It consists of seven questions and is calculated by assigning scores of 0, 1, 2, and 3, to the response categories of “not at all”, “several days”, “more than half the days,” and “nearly every day,” respectively (see Appendix V).

iv. Clinical Global Impression (CGI)

The Clinical Global Impression Scale (CGI) is a brief clinician-rated instrument that consists of three different global measures (see Appendix VI):

- Severity of illness: overall assessment of the current severity of the patient's symptoms (CGI-S);
- Global improvement: overall comparison of the patient's baseline condition with his current state (CGI-I);
- Efficacy index: overall comparison of the patient's baseline condition to a ratio of current therapeutic benefit and severity of side effects (CGI-EI).

v. Changes to initial prescribing based on availability of pharmacogenomic data

The influence of pharmacogenomic data on a physician's initial prescription for both GEN and E-GEN will be evaluated by documenting the psychotropic medication prescribed before the availability of the pharmacogenomics data. This will be compared to changes (if any) to the physician's prescription when pharmacogenomics data becomes available.

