#### **3.2 Analysis Populations**

##### **3.2.1 Per Protocol (PP) Population**

The primary statistical analysis will be performed using the Per Protocol (PP) principle. The population of this analysis will be all subjects who met the inclusion and exclusion criteria. Other variables relating to exclusion may include but are not limited to:

At screening:

- a) Meets all inclusion/exclusion criteria (except exception 8 and 13)
- b) All assessments completed by appropriate person
- c) QIDS-C16 and -SR16 are  $\geq 11$

At baseline:

- a) Confirmation that subject still satisfies all Inclusion/Exclusion criteria
- b) Randomization occurred prior to the Baseline visit

- c) All assessments completed by appropriate person. The Blinded Rater should administer the QIDS-C16, not the Treating Clinician.
- d) Baseline was completed within 42 days of screening
- e) Sample was received and report was released (GEN & E-GEN) prior to baseline
- f) Report was viewed (GEN & E-GEN) at/prior to baseline
  - o If report not viewed at/prior to baseline, prescription decision date must follow view date of report
- g) Baseline QIDS-SR is  $\geq 11$
- h) Baseline HAM-D-17  $\geq 14$

After enrollment:

- a) Week 4 visit occurs within 20-36 days of baseline visit
- b) Week 8 visit occurs within 48-64 days of baseline visit
- c) QIDS-C16 completed by Blinded Rater, not Treating Clinician
- d) Subject did not start ECT, DBS, or TMS
- e) MDD Rx given by study affiliated clinician
- f) If unblinding occurs before week 8 visit, data is not included in PP population

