### **3.2.2 Intention to Treat (ITT) Population**

The population for this analysis will be all subjects who met the inclusion and exclusion criteria at screening, and were randomized. Subjects that meet inclusion and exclusion criteria and were randomized but have low baseline QIDS-SR scores will be included in ITT analysis.

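### GAD-7 remission, response and percentage change carry no baseline condition: patients already below 5 count as remitters even if they worsen, and a baseline of 0 cannot be analysed

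*SAP*

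**What the plan says.** SAP 7.2 begins "A remitter is defined as a participant at a post-treatment visit with HAM-D17" and lists the cut-offs: HAM-D17 ≤7, HAM-D6 <5, QIDS-SR ≤5, PHQ-9 <5, GAD-7 <5, CGI-S ≤1. All apply to the post-treatment score only. SAP 7.1 covers several scales, GAD-7 among them, with one rule: "a responder is defined as a participant with 50% decrease from baseline in total scale score". Neither section says what to do with a baseline that is already low, or that is 0.

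SAP 2.1.4 places GAD-7 among the exploratory objectives, with "Mean percentage change in Generalized Anxiety Disorder 7-item (GAD-7) scale from baseline to end of Week 8" and later visits, and "Percentage of responders and remitters at Week 8, Week 12, Month 6, Month 9, Month 12 on GAD-7". SAP 5.2 sends GAD-7 percentage change to the same analysis as the primary variable. The divisor is defined in Protocol 16.1.3: y1 "is the baseline score for each participant for each rating scale". Protocol 8.2.1 describes GAD-7 as "calculated by assigning scores of 0, 1, 2, and 3, to the response categories" over seven questions, so totals run from 0 to 21.

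On populations, SAP 3.2.1 states "The primary statistical analysis will be performed using the Per Protocol (PP) principle" and requires baseline HAM-D17 ≥14 and QIDS-SR ≥11. SAP 3.2.2 sets neither floor, and says that otherwise eligible randomized patients who "have low baseline QIDS-SR scores will be included in ITT analysis". Under SAP 5.2, ITT versions of the secondary analyses are optional. Protocol 6.2.1 sets entry severity on QIDS-C16 and QIDS-SR16 only.

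**The concern.** Remission should mean moving from above a threshold to below it. With no baseline condition, a patient who never had notable anxiety is a remitter for as long as the score stays under 5. Such patients raise the GAD-7 remission rate in every arm and pull the ratio between arms towards 1.

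Percentage change has a related weakness. At a baseline of 0 the patient has no computable outcome at any visit and drops out of the model, yet is still counted in the remission analysis. At a baseline of 1 or 2, a small worsening becomes a very large positive percentage, while improvement can never exceed 100%. A few such patients can move the mean.

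SAP 1.1 expects the results to inform guidelines and to support a health technology application, where absolute remission rates are read at face value.

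**Working it through.** The plan states no figure for this point, so there is nothing to reproduce. The check has four steps.

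**1. Remission cut-offs against baseline floors** (SAP 7.2, 3.2.1, 3.2.2)

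| Scale | Remission | PP floor | Already remitted at baseline in PP? |
|---|---|---|---|
| HAM-D17 | ≤7 | ≥14 | Impossible |
| QIDS-SR | ≤5 | ≥11 | Impossible |
| HAM-D6 | <5 | none | Possible by arithmetic |
| PHQ-9 | <5 | none | Possible, unlikely |
| CGI-S | ≤1 | none | Possible, unlikely |
| GAD-7 | <5 | none | Possible |

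For HAM-D6, the item maxima in Protocol Appendix II sum to 52 for HAM-D17. The six HAM-D6 items (1, 2, 7, 8, 10, 13) sum to 4+4+4+4+4+2 = 22, which leaves 52 − 22 = 30 for the other eleven. HAM-D17 = 14 therefore does not guarantee HAM-D6 ≥5.

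**2. The GAD-7 rules applied as written**, with percentage change = (y2 − y1)/y1 × 100

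| Baseline → post | % change | 50% response | Remitter (<5) |
|---|---|---|---|
| 3 → 4 | +33% | no | yes |
| 4 → 4 | 0% | no | yes |
| 1 → 4 | +300% | no | yes |
| 0 → 3 | undefined | undefined; no if coded post ≤ 0.5 × baseline | yes |
| 0 → 0 | undefined (0/0) | undefined; yes if coded post ≤ 0.5 × baseline | yes |

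In a simple mean, one patient going from 1 to 4 (+300%) cancels ten patients going from 10 to 7 (10 × −30% = −300%), although each moved by 3 points.

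**3. How many patients might be affected.** The documents do not say. Assume a normal baseline, rounded to whole scores, with negative values set to 0. The share below 5 is Φ((4.5 − mean)/SD) and the share at 0 is Φ((0.5 − mean)/SD).

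| Assumed mean, SD | Below 5 | At 0 |
|---|---|---|
| 10, 5 | Φ(−1.10) = 13.6% | Φ(−1.90) = 2.9% |
| 12, 5 | Φ(−1.50) = 6.7% | Φ(−2.30) = 1.1% |
| 14, 4.5 | Φ(−2.11) = 1.7% | Φ(−3.00) = 0.1% |

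With 190 per arm (Protocol 10.0), that is about 3 to 26 patients per arm below 5, and at most 5 or 6 at 0. The PP set would have fewer.

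**4. Effect on the remission contrast.** Let q be the share already below 5, k the share of those who stay there, and p the true remission rate among the rest. The observed rate is (1 − q)p + qk. Assume p = 20% versus 30% (difference 10 points, ratio 1.50) and k = 0.70 to 0.85, equal across arms. The difference is then (1 − q) × 10 points.

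| q | Observed rates, k = 0.70 | Observed rates, k = 0.85 | Difference | Ratio |
|---|---|---|---|---|
| 2% | 21.0 vs 30.8% | 21.3 vs 31.1% | 9.8 | 1.47 to 1.46 |
| 5% | 22.5 vs 32.0% | 23.3 vs 32.8% | 9.5 | 1.42 to 1.41 |
| 10% | 25.0 vs 34.0% | 26.5 vs 35.5% | 9.0 | 1.36 to 1.34 |
| 14% | 27.0 vs 35.6% | 29.1 vs 37.7% | 8.6 | 1.32 to 1.30 |

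A second illustration uses other assumptions: 10% versus 20% true remission, 190 per arm, two-sided 0.05, q = 10%, all of whom stay below. The observed rates are 0.10 + 0.90 × 10% = 19% and 0.10 + 0.90 × 20% = 28%, with power of about 54%. Restricting to the 171 per arm at risk keeps 10% versus 20%, with power of about 74%.

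**The case against.** **Scope.** SAP 7.2 names HAM-D17 first, so a reader might infer that remission is inflated on every scale, including HAM-D17 remission, a leading secondary objective. The documents do not support that. In the PP set, which carries the main conclusions, the baseline floors rule it out for HAM-D17 and QIDS-SR. Exposure on those two scales is confined to ITT secondary analyses, which are optional. Those patients also had QIDS-SR ≥11 at screening, and their psychotropic medication, benzodiazepines apart, was meant to stay unchanged until baseline. On PHQ-9, HAM-D6 and CGI-S, entry requires a DSM-IV-TR major depressive episode, so scores in the remitted range at baseline should be rare. This part of the objection stands.

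**Planned safeguards.** SAP 5.1 and 5.2 provide Huber robust regression, and the model contains the baseline score. Robust regression is specified for the complete-case analysis, not for the mixed model for repeated measures (MMRM). It can down-weight +300%, but it cannot supply a value for a zero divisor. A linear baseline term does not remove the instability of dividing by a small baseline.

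**Post-treatment status as an endpoint.** The share scoring under 5 after treatment is a coherent quantity, and randomization balances those already low on average. That defends the comparison against bias, but not the label remission for a patient who worsened, nor the diluted ratio.

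**Restricting on baseline.** Baseline follows randomization, and the unblinded clinician may already hold the report, so the restriction is formally post-randomization selection. The risk is limited: Protocol 9.3 places the assessments before any antidepressant change, and Protocol 13.0 blinds patients and assessors.

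**Conclusion.** The point holds for GAD-7, in PP and in ITT. Followed exactly, the definitions classify some patients who worsen as remitters, leave percentage change and response undefined at a baseline of 0, and give extreme percentages just above 0. These statements need no assumption. The size does: with 2% to 14% of patients below 5 at baseline, a 10-point difference falls to between 9.8 and 8.6 points and a ratio of 1.50 to between about 1.47 and 1.30. The baseline distribution, true remission rates and share staying below 5 are all assumed. Heavier dilution would need more low-anxiety patients than these assumptions give, and the documents do not support claiming it.

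Elsewhere the problem is small or absent. HAM-D17 and QIDS-SR are safe in PP, and exposure on PHQ-9, HAM-D6 and CGI-S is possible but expected to be minor. The primary endpoint, HAM-D17 percentage change in PP, is untouched. Since GAD-7 is exploratory, this is a worthwhile correction of low severity.

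**What to change.** - **SAP 5.2 (and the matching entries in 2.1.4 and 2.2.3):** analyse GAD-7 as absolute change from baseline, with baseline GAD-7 as covariate, instead of percentage change. Every patient with a baseline score can then enter the model, including those at 0.
- **SAP 7.1 and 7.2:** analyse GAD-7 response and remission among patients with baseline GAD-7 ≥5. Keep remission as post-treatment GAD-7 <5, and report by arm the number not at risk.
- **Other scales:** if remission is reported in ITT, show it also among patients who did not meet that scale's own SAP 7.2 remission criterion at baseline. Use each criterion as written, since some are strict and some are not.

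The change is to SAP wording and uses scores already collected. The costs are slightly smaller, scale-specific denominators, and selection on a baseline measured after randomization, although before any antidepressant change and in blinded patients.
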